**Table 2 Administration of First and Subsequent Infusions of DHES0815A**

	Cycle 1	Cycle 2	Cycle 3 and Beyond
Infusion time	90 minutes	30 minutes	30 minutes
Observation time	2 hours	2 hours	30 minutes

Notes:

Infusion and observation times assume that no infusion-related adverse events occurred during the prior infusion. If no infusion-related adverse event occurred during the first infusion, the infusion time for Cycle 2 can be shortened to 30 minutes, but the observation time should remain at 2 hours. If no infusion-related adverse events have occurred after the first two cycles, both the infusion time and the observation time can be shortened to 30 minutes.

If a patient experiences an infusion-related reaction, refer to Section [5.1.1.10](#) for details on management.

#### **4.3.3        Investigational Medicinal Product Accountability**

All IMPs required for completion of this study (DHES0815A) will be provided by the Sponsor where required by local health authority regulations. The study site will acknowledge receipt of IMPs supplied by the Sponsor using the IxRS to confirm the shipment condition and content. Any damaged shipments will be replaced.

IMPs will either be disposed of at the study site according to the study site's institutional standard operating procedure or be returned to the Sponsor (if supplied by the Sponsor) with the appropriate documentation. The site's method of destroying Sponsor-supplied IMPs must be agreed to by the Sponsor. The site must obtain written authorization from the Sponsor before any Sponsor-supplied IMP is destroyed, and IMP destruction must be documented on the appropriate form.

Accurate records of all IMPs received at, dispensed from, returned to, and disposed of by the study site should be recorded on the Drug Inventory Log.

#### **4.3.4        Continued Access to DHES0815A**

The Sponsor (Genentech, a member of the Roche Group) will offer continued access to Genentech IMP (DHES0815A) free of charge to eligible patients in accordance with the Roche Global Policy on Continued Access to Investigational Medicinal Product, as outlined below.

A patient will be eligible to receive Genentech IMP (DHES0815A) after completing the study if all of the following conditions are met:

- The patient has a life-threatening or severe medical condition and requires continued Genentech IMP treatment for his or her well-being
- There are no appropriate alternative treatments available to the patient
- The patient and his or her doctor comply with and satisfy any legal or regulatory requirements that apply to them

A patient will not be eligible to receive Genentech IMP (DHES0815A) after completing the study if any of the following conditions are met:

- The Genentech IMP is commercially marketed in the patient's country and is reasonably accessible to the patient (e.g., is covered by the patient's insurance or wouldn't otherwise create a financial hardship for the patient)
- The Sponsor has discontinued development of the IMP or data suggest that the IMP is not effective for advanced and/or metastatic HER2-positive BC
- The Sponsor has reasonable safety concerns regarding the IMP as treatment for advanced and/or metastatic HER2-positive BC
- Provision of the Genentech IMP is not permitted under the laws and regulations of the patient's country

The Roche Global Policy on Continued Access to Investigational Medicinal Product is available at the following Web site:

[http://www.roche.com/policy\\_continued\\_access\\_to\\_investigational\\_medicines.pdf](http://www.roche.com/policy_continued_access_to_investigational_medicines.pdf)

#### **4.4 CONCOMITANT THERAPY**

Concomitant therapy consists of any medication (e.g., prescription drugs, over-the-counter drugs, vaccines, herbal or homeopathic remedies, nutritional supplements) used by a patient in addition to protocol-mandated treatment from 7 days prior to initiation of study drug to the study completion/discontinuation visit. All such medications should be reported to the investigator and recorded on the Concomitant Medications eCRF.

##### **4.4.1 Permitted Therapy**

Patients are permitted to use the following therapies during the study:

- Oral contraceptives, hormone-replacement therapy, or other maintenance therapy
- Hematopoietic growth factors such as erythropoietin, granulocyte colony-stimulating factor (filgrastim, pegfilgrastim), and granulocyte-macrophage colony-stimulating factor (sargramostim) as clinically indicated and when used in accordance with instructions provided in the package inserts.

Any use of these agents during the DLT assessment window must be discussed with the Medical Monitor.

- Bisphosphonates and denosumab for prevention of skeletal-related events as clinically indicated and when used in accordance with instructions provided in the package inserts
- Biologic agents (other than those listed above and not intended for the treatment of cancer) as clinically indicated and when used in accordance with instructions provided in the package inserts

In general, investigators should manage a patient's care with supportive therapies as clinically indicated, per local standard practice.

#### **4.4.2      Cautionary Therapy**

##### **4.4.2.1      Medications Given with Precaution due to Effects Related to Cytochrome P450 Enzymes**

DHES0815A consists of a human monoclonal IgG1 antibody, a cleavable disulfide-linker, and PBD-MA. There is a low risk of PK drug–drug interactions (DDI) between the MAb component and small molecules due to different metabolic pathways that each undergo. In vitro data also suggest there is low risk of DDI specifically with the released payload from DHES0815A, unconjugated PBD-MA. PBD-MA was found to be a weak competitive inhibitor of CYP2C8 and CYP3A4/5 and a time-dependent inhibitor for CYP3A4/5 as well as CYP2B6 at concentrations much higher than expected to be reached given the projected administered clinical doses of DHES0815A. Given that the expected liver concentration of the PBD-MA will likely be low at the administered clinical dose, the DDI potential for the unconjugated PBD-MA as a perpetrator is likely low. In human and animal liver microsomes the unconjugated PBD-MA was extensively metabolized by oxidation pathways, which are catalyzed mainly by CYP3A4/5 as well as CYP2J2 (minor). However, in vivo contribution of CYP3A to the total clearance of unconjugated PBD-MA following administration of DHES0815A is not known at this time. Therefore, the DDI potential for unconjugated PBD-MA is unclear as a victim and the use of strong CYP3A inhibitors should be avoided in patients who are administered DHES0815A. Patients should be closely monitored for adverse reactions if taking strong CYP3A inhibitors cannot be avoided; these include, but are not limited to, boceprevir, clarithromycin, conivaptan, indinavir, itraconazole, ketoconazole, mibefradil, lopinavir/ritonavir, nefazodone, nelfinavir, ritonavir, posaconazole, saquinavir, telaprevir, telithromycin, or voriconazole. Investigators may also consult the Drug Development and Drug Interactions: Table of Substrates, Inhibitors, and Inducers web site for a non-exhaustive list of CYP3A:

<https://www.fda.gov/Drugs/DevelopmentApprovalProcess/DevelopmentResources/DrugInteractionsLabeling/ucm093664.htm>

#### **4.4.3      Prohibited Therapy**

Use of the following concomitant therapies is prohibited during the study:

- Cytotoxic chemotherapy
- Radiotherapy for progressive disease except for cases where localized radiotherapy is indicated and approval of the Medical Monitor is obtained
- Immunotherapy for the treatment of cancer
- Hormone therapy (other than contraceptives, hormone-replacement therapy, or megestrol acetate)
- Biologic agents for the treatment of cancer
- Herbal therapy
- Any therapies intended specifically for the treatment of advanced cancer, whether approved by regulatory authorities or investigational

Patients who require the use of any of these agents will be discontinued from DHES0815A treatment. Questions about whether specific medications are prohibited therapy during this Phase I study should be discussed with the Medical Monitor.

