#### **4.1.2 Exclusion Criteria**

Patients who meet any of the following criteria will be excluded from study entry:

- Treatment with chemotherapy, hormonal therapy (except hormone replacement therapy, oral contraceptives), immunotherapy, biologic therapy, radiation therapy (except palliative radiation to bony metastases), or herbal therapy as cancer therapy within 4 weeks prior to initiation of DHES0815A.

A shorter interval may be acceptable for patients on oral endocrine therapy provided that any clinically relevant drug-related toxicity has completely resolved and prior approval is obtained from the Medical Monitor.

*For lapatinib, a 14-day washout is adequate on the condition that any related toxicities have resolved to Grade ≤1 or baseline prior to initiation of DHES0815A.*

- Treatment with any other ADC compound containing a DNA-damaging agent (i.e., topoisomerase inhibitors, DNA alkylators), including but not limited to DS-8201a, SYD-982, and ADCT-502 at any time prior to initiation of DHES0815A  
Trastuzumab emtansine is not considered a DNA-damaging agent.
- History of exposure to the following cumulative doses of anthracycline as specified below:

Doxorubicin > 500 mg/m^2  
 Liposomal doxorubicin > 500 mg/m^2  
 Epirubicin > 720 mg/m^2  
 Mitoxantrone > 120 mg/m^2  
 Idarubicin > 90 mg/m^2

If another anthracycline or more than one anthracycline has been used, then the cumulative dose must not exceed the equivalent of 500 mg/m^2 of doxorubicin.

- History of severe allergic or anaphylactic reactions to monoclonal antibody therapies (or recombinant antibody-related fusion proteins)
- Pregnancy, lactation, or breastfeeding
- Major surgical procedure within 4 weeks prior to Day 1
- Evidence of a significant uncontrolled concomitant disease of the nervous system, pulmonary (including obstructive pulmonary disease and history of symptomatic bronchospasm), autoimmune, renal, hepatic, endocrine, or gastrointestinal disorders; or a serious non-healing wound or fracture

*Note: Patients with vascular leak syndrome or with a history of or who have active interstitial lung disease or pulmonary fibrosis or other clinically significant lung disease are not eligible for the study.*

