### **4.6 TREATMENT, PATIENT, STUDY, AND SITE DISCONTINUATION**

#### **4.6.1 Study Treatment Discontinuation**

Patients must permanently discontinue study treatment if they experience any of the following:

- Any medical condition that the investigator or Sponsor determines may jeopardize the patient's safety if he or she continues to receive study treatment
- Investigator or Sponsor determines it is in the best interest of the patient
- Pregnancy
- Use of an anti-cancer therapy other than DHES0815A
- Symptomatic deterioration attributed to disease progression
- Confirmed disease progression per investigator assessment according to RECIST v1.1 unless a patient continues to demonstrate signs and symptoms of clinical benefit from DHES0815A treatment that is independent of RECIST v1.1, as judged by the investigator and upon discussion with the Medical Monitor (see [Appendix 3](#))

The primary reason for study treatment discontinuation should be documented on the appropriate eCRF. Patients who discontinue study treatment prematurely will not be replaced unless enrolled in the dose-escalation cohorts and they discontinue prior to completion of the 21-day DLT window.

Patients will return to the clinic for a treatment discontinuation visit within 42 days after the last dose of study drug (see [Appendix 1](#) for additional details).

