#### **5.3.1 Adverse Event Reporting Period**

Investigators will seek information on adverse events at each patient contact. All adverse events, whether reported by the patient or noted by study personnel, will be recorded in the patient's medical record and on the Adverse Event eCRF.

After informed consent has been obtained but prior to initiation of study drug, only serious adverse events caused by a protocol-mandated intervention (e.g., invasive procedures such as biopsies, discontinuation of medications) should be reported (see Section 5.4.2 for instructions for reporting serious adverse events).

After initiation of study drug, all adverse events will be reported until 42 days after the last dose of study drug or until the patient is lost to follow-up, withdraws consent, initiates another anti-cancer therapy, or until study discontinuation/termination, whichever occurs first.

Instructions for reporting adverse events that occur after the adverse event reporting period are provided in Section 5.6.

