#### **5.4.2.2 Events That Occur after Study Drug Initiation**

After initiation of study drug, serious adverse events and adverse events of special interest will be reported until 42 days after the last dose of study drug or until the patient is lost to follow-up, withdraws consent, initiates another anti-cancer therapy, or study discontinuation/termination, whichever occurs first. DLTs will be reported during the DLT assessment window. Investigators should record all case details that can be gathered immediately (i.e., within 24 hours after learning of the event) on the Adverse Event eCRF and submit the report via the EDC system. A report will be generated and sent to Safety Risk Management by the EDC system.

In the event that the EDC system is unavailable, the paper Clinical Trial Serious Adverse Event/Adverse Event of Special Interest Reporting Form provided to investigators should be completed and submitted to the Sponsor or its designee immediately (i.e., no more than 24 hours after learning of the event) by faxing the form using the fax number provided to investigators in Section [5.4.2.1](#). Once the EDC system is available, all information will need to be entered and submitted via the EDC system.

Instructions for reporting serious adverse events that occur after the adverse event reporting period are provided in Section [5.6](#).

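### Sections 4.4.3 and 4.6.1 disagree on whether DHES0815A continues after approved localized radiotherapy, and on one reading adverse event reporting closes while the drug is still being given

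*Combined protocol and SAP*

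**What the plan says.** **Whether treatment continues.** Section 4.4.3 (Prohibited Therapy) lists "Radiotherapy for progressive disease except for cases where localized radiotherapy is indicated and approval of the Medical Monitor is obtained". It then states: "Patients who require the use of any of these agents will be discontinued from DHES0815A treatment". Approved localized radiotherapy is outside that list, so 4.4.3 alone gives no reason to stop DHES0815A.

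Section 4.6.1 opens its list with "Patients must permanently discontinue study treatment if they experience any of the following", and one item is "Use of an anti-cancer therapy other than DHES0815A". That item has no exception and does not refer to 4.4.3. The progression item in the same list does carry an exception: "unless a patient continues to demonstrate signs and symptoms of clinical benefit from DHES0815A treatment that is independent of RECIST v1.1".

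**When reporting ends.** Section 5.3.1 runs adverse event reporting to 42 days after the last dose, or to an earlier stop if the patient, among other things, "initiates another anti-cancer therapy, or until study discontinuation/termination, whichever occurs first". Section 5.4.2.2 applies the same stop to serious events and events of special interest: "withdraws consent, initiates another anti-cancer therapy, or study discontinuation/termination, whichever occurs first". Section 5.6 and Appendix 1 footnote i repeat it. None of the four makes the stop conditional on DHES0815A having ended.

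**How the term is used.** The protocol does not define anti-cancer therapy. The nearest guide is the washout criterion in 4.1.2, whose list includes "radiation therapy (except palliative radiation to bony metastases), or herbal therapy as cancer therapy within 4 weeks prior to initiation".

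**How the data are used.** Section 6.4.1 counts as treatment-emergent whatever is reported in the reporting period. It also says that events from Day 1 of treatment onward are summarized, and that safety data accumulate to the end of treatment.

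**The concern.** Two sites could handle the same patient differently and both cite the protocol. One continues DHES0815A under 4.4.3 and the other stops it under 4.6.1. Number of cycles and dose intensity are endpoints of the primary safety objective (Table 1), so the choice reaches the primary data.

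The second issue is data capture. If the patient continues, and the radiotherapy is also taken as the start of another anti-cancer therapy, the reporting period closes while infusions go on. After that, 5.6 asks only for serious events believed related to study drug. Non-serious events, and serious events judged unrelated, are no longer required, and later events drop out of the treatment-emergent definition. In a first-in-human study with cohorts of 3–6 patients, later-cycle toxicity at a dose level rests on few patients, and the RP2D is chosen on the totality of data (Section 3.1.1.3).

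**Working it through.** The plan gives no figure to reproduce. The check sets the sections side by side and asks which readings produce which result.

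**Step 1. Can the situation arise?** The 4.4.3 exemption concerns radiotherapy for progressive disease. Section 4.6.1 lets a patient with confirmed progression continue when clinical benefit persists, after discussion with the Medical Monitor, and 3.1.1.4 also accepts benefit judged independently of RECIST. Dosing alongside such radiotherapy is therefore possible under the protocol.

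**Step 2. Readings of the text.**

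| Is approved localized radiotherapy anti-cancer therapy? | Which section governs stopping? | DHES0815A | Reporting period | Result |
|---|---|---|---|---|
| No | No conflict | Continues | To 42 days after last dose | No gap |
| Yes | 4.6.1 | Stops | Ends when radiotherapy starts | No dosing outside the period, but the 4.4.3 exemption has no effect for a patient on treatment |
| Yes | 4.4.3, with the 5.3.1 stop applied as written | Continues | Ends when radiotherapy starts | Dosing outside the period |
| Yes | 4.4.3, taken to override the 5.3.1 stop too | Continues | To 42 days after last dose | No gap, but no text says this |

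The documents do not select a row. Only the third row gives dosing outside the reporting period.

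**Step 3. What else applies in the third row?** Appendix 1 schedules adverse event assessment on Day 1 of every cycle, including cycles beyond Cycle 8. Section 4.5 requires scheduled activities to be done and documented, and toxicity to be assessed before each dose. Section 5.3.1 itself opens by asking for adverse events at every patient contact. Some events would therefore still be recorded. They would lie outside the defined period, while 6.4.1 both restricts treatment-emergent events to that period and says that safety data run to the end of treatment.

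**Step 4. Length, for illustration only.** Inputs: a 21-day cycle (Section 3.1) and 42 days of reporting after the last dose (5.3.1). Assume that radiotherapy starts on a dosing day and the last dose is k cycles later. The period then closes 21k + 42 days earlier than under the 42-day rule:

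- k = 1: 21 + 42 = 63 days
- k = 2: 42 + 42 = 84 days
- k = 3: 63 + 42 = 105 days
- k = 4: 84 + 42 = 126 days

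Only 21k of these days fall before the last infusion. The other 42 are follow-up. The documents do not say how long dosing may continue, so no value of k is preferred.

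**The case against.** The strongest reply is that the gap needs one term read two ways. If approved radiotherapy is anti-cancer therapy, 4.6.1 stops the drug. If it is not, the 5.3.1 stop never applies. Either consistent reading leaves nobody dosed outside the period.

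Other passages also suggest that the reporting stop was meant for the next line of treatment. Appendix 1 footnote d pairs it with subsequent therapies, 4.5.11.3 speaks of the next therapy, and 5.6 refers to study drug as already past. The evidence in 4.1.2 is limited too: it excepts palliative radiation to bone, and its closing words about cancer therapy may qualify only herbal treatment.

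Most of this stands. A reader might infer that 4.6.1 forces every irradiated patient off drug. The text does not establish that, because the trigger is undefined. A reader might also infer that toxicity will be under-counted, by 105 days for example. The text does not establish that either: the loss depends on the third row of the table, scheduled assessments continue, and 105 days is the case k = 3, of which 42 days are after dosing.

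What the reply does not remove is the conflict. Treating radiotherapy for progressive disease as something other than anti-cancer therapy is not the natural reading, and letting 4.6.1 govern leaves the 4.4.3 exemption without effect on treatment. Letting the specific exemption override the general rule is reasonable, but no text says so, and it leads to the third row unless the reporting stop is overridden as well.

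**Conclusion.** The point holds in a limited form. Sections 4.4.3 and 4.6.1 give different answers on continuing DHES0815A after approved localized radiotherapy for progressive disease, and the term on which the answer turns is undefined. If that radiotherapy is anti-cancer therapy and the patient stays on drug under 4.4.3, the four reporting passages literally close the period during dosing. That contradicts the on-treatment assessments in Appendix 1 and the 6.4.1 statement on accumulating safety data to the end of treatment.

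The number of affected patients cannot be derived from the documents and is probably small, since each case needs progressive disease, continued dosing and Medical Monitor approval. Palliative bone radiation is the least certain subset. Dose-escalation DLT counts would ordinarily be untouched: the DLT window is Cycle 1, and the first scheduled on-study tumor assessment is in the last week of Cycle 2. The exposed data are later-cycle adverse events, cycles received and dose intensity. This should be corrected, but it does not undermine the design. Nothing here says which treatment rule is right.

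**What to change.** 1. Reconcile 4.4.3 and 4.6.1 so that both say the same about Medical Monitor-approved localized radiotherapy. The direction is for the sponsor's clinical team.
2. Use anti-cancer therapy with one stated meaning throughout, including whether localized radiotherapy, and palliative bone radiation in particular, falls within it.
3. Whatever is decided under 1, amend 5.3.1, 5.4.2.2, 5.6 and Appendix 1 footnote i so that another anti-cancer therapy ends the reporting period only if it starts after the last dose of DHES0815A. This concerns data capture, not treatment. It prevents the start of another therapy from ending reporting while study drug is being given, and the treatment-emergent definition in 6.4.1 then follows without further change.

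The cost is wording in five or six places (four for the reporting period, one or two for the treatment rule) and slightly more adverse event entry for the patients concerned. No sample size or analysis method changes.

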## **4.5 STUDY ASSESSMENTS**

The schedule of activities to be performed during the study is provided in [Appendix 1](#). All activities must be performed and documented for each patient.

Patients will be closely monitored for safety and tolerability throughout the study. Patients should be assessed for toxicity prior to each dose; dosing will occur only if the clinical assessment and local laboratory test values are acceptable.

Collection of any non-safety-related data or patient samples may be terminated by the Sponsor at any time if further collection of such data or samples is also not related to the study's primary objective(s). The decision to discontinue any data collection will be communicated to sites (IRBs and ECs) by means of a memorandum and will not require a protocol amendment.

